7. EFFICACY AND SAFETY CRITERIA

7.1. Efficacy Criteria

Diagnostic accuracies of 18F-PSMA PET and mpMRI will be calculated by means of sensitivity: true positive/(true positive + false negative); specificity: true negative/(false positive + true negative); PPV: true positive/(true positive + false positive); and NPV: true negative/(true negative + false negative) using the prostate biopsy result as reference standard

7.2. Safety Criteria

A large amount of evidence shows that ¹⁸F-PSMA is well tolerated, and it is not associated with serious adverse events (SAE) (6). Drug's reaction could occur, in a very small percentage of the population as it is reported in the normal clinical practice. Patients presenting contraindication to PET/MRI examination will be excluded from the study a priori. More details on this can be found in the section "Exclusion criteria" of this protocol.

8. TRIAL DESIGN

In this single-arm phase II, prospective, monocentric study we will test whether addition of 18F-PSMA PET scan to mpMRI helps improving the diagnostic pathway efficiency in identifying those men who should necessarily undergo TBx, because of high-risk to harbor csPCa.

Furthermore, the combined use of 18F-PSMA PET and mpMRI for the diagnosis of PCa may also result in a reduced number of follow-up procedures in those patients who can safely avoid a prostate biopsy given the very low risk of harboring csPCa using a single, one-stop approach with both imaging modalities. A more efficient pre-biopsy triage test using the fully hybrid 18F-PSMA PET/MRI might result in the reduction of the total number of biopsies for men with a clinical suspicion of PCa, reducing also patient discomfort combining two different diagnostic procedures in one single step and avoiding, whenever possible, the biopsy-related side effects.

A total of 167 consecutive patients with a clinical suspicion of csPCa (defined as the presence of PCa with ISUP grade equal or higher to 2), referred to simultaneous 18F-PSMA PET/MRI with mpMRI, will be identified and enrolled. PET/MRI images will be qualitatively and quantitatively evaluated by an experienced Nuclear Medicine and an experienced Radiologist physicians. In particular, for qualitative evaluation, lesions classified as PI-RADS higher or equal to 3 on mpMRI images and/or showing pathologically increased 18F-PSMA uptake on PET images, will be considered as positive for csPCa. All men will then receive a prostate biopsy (12-core random systematic prostate biopsy plus eventual targeted biopsy) as back-up histology according to the results of PET/MR imaging.

Specifically, patients with both positive mpMRI and 18F-PSMA PET, defined as the presence of one or more lesions with PI-RADS higher or equal to 3 and an increased uptake of 18F-PSMA, will receive a 12-core random systematic prostate biopsy (TRUS-Bx) in addition to MRI targeted biopsy (MRI-TBx) and 18F-PSMA PET targeted biopsy (PSMA PETTBx).

Patients with both negative mpMRI and 18F-PSMA PET scan will receive a 12-core TRUS-Bx. Patients with only positive mpMRI will receive MRI-TBx and 12-core TRUSBx. Patients with only positive 18F-PSMA PET will receive 18F-PSMA PET-TBx and 12-core TRUSBx. MRI-TBx will be performed by means of a fusion software-assisted approach using the Biojet system taking 4 cores in any mpMRI suspicious areas. PSMA PET-TBx will be performed taking 4 cores in the area of the prostate showing an increased tracer uptake. All prostate biopsy specimens will be evaluated by fully dedicated uro-pathologist.

In order to calculate accuracy, sensitivity, specificity, positive predictive value and negative predictive value of 18F-PSMA PET/MRI for the identification of csPCa, 18F-PSMA PET/MRI findings will be correlated with histopathological samples gathered with prostate biopsy.

The proportion of csPCa missed by PSMA PET scan or mpMRI alone will be then calculated.

In order to study the proportion of unnecessary biopsies that could be spared by adding 18F-PSMA PET to mpMRI in the triage phase, only patients with positive mpMRI and negative 18F-PSMA PET scan will be considered for the analysis and the proportion of clinically insignificant PCa detected in this subset of patients will be assessed. In this way we will identify proportion of unnecessary prostate biopsies that could have been spared, thus reducing overdiagnosis.

Furthermore, the potential role of quantitative PET and mpMRI parameters in identifying csPCa will be investigated. Specifically, recently emerging radiomic features will be evaluated, together with PET- and MRI-derived quantitative conventional imaging parameters, and regression analyses will be used for evaluating their role in predicting histopathological data. To assess the diagnostic performance of PET and MRI parameters, ROC curve analysis will be performed to select optimal cut-offs in predicting the presence of csPCa as defined by cytological examination and the corresponding diagnostic accuracy will be computed (more detailed information in the section "Statistics" of this protocol). No interim analyses are planned.

The following measures will be taken in order to minimize the risk of bias:

MpMRI is the standard of care diagnostic tool for staging and restaging in patients with Pca. The high expertise of the Center in prostate MRI has shown negligible inter-reader variability. All MRIs will be analysed by an experienced Radiologist (6 years of experience in prostate mpMRI). All PET exams will be analysed by an expert Nuclear Medicine physician (>10 years of experience in prostate PET). Furthermore, to avoid bias in the qualitative image analysis, PET and mpMR scans will be evaluated blind to the results of the other imaging modality. For efficacy analyses that require complete patient data, missing values during the treatment period will be replaced, for all variables, with the LOCF technique (Last Observation Carried Forward). Imputed values will be included in the analysis set(s), but will not change the original clinical database. For subjects who interrupt prematurely the trial due to the "adverse event", the BOCF technique (Basal Observation Carried Forward) will be used instead of the LOCF, in order to avoid the allocation of a positive result to patients to be considered treatment failures.

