2. SYNOPSIS

Trial Title	Fully hybrid 18F-PSMA PET/MRI as one-stop approach for the diagnosis of clinically significant prostate cancer	
Protocol Acronym/Number	RF-2021-12372278	
Protocol Version and Date	v2.0, 30 GEN 2023	
EudraCT number	NA	
Sponsor	IRCCS Ospedale San Raffaele [name]	
Funding Source(s)	Italian Ministry of Health	
Principal Investigator	[name], U.O. of Nuclear Medicine	
Trial Description	
This project aims to evaluate the role of fully hybrid PET/MRI with 18F-PSMA and multiparametric MR imaging (mpMRI) as one-stop approach for the diagnosis of clinically significant prostate cancer (csPCa).
 
Our main hypothesis is that adding 18F-PSMA PET to mpMRI prior to biopsy, will reduce the number of false negative findings, while at the same time, allowing also to reduce the number of unnecessary prostate biopsies in patients with low-risk, clinically indolent PCa.
	
	Primary	Secondary
Objectives	To assess the accuracy and the predictive value of fully hybrid 18F-PSMA PET/MRI for the diagnosis of csPCa	
 1) To compare the proportion of csPCa missed by 18F-PSMA PET scan or mpMRI alone 2) To report the reduction in the detection of clinically insignificant PCa when combining mpMRI and 18F-PSMA PET, and consequently the proportion of unnecessary biopsies potentially spared.
Endpoints	Diagnostic accuracy measured with sensitivity, specificity, positive and negative predicted value	
 1) The number of csPCa missed by PET and MR imaging when read independently 2) Only in patients with positive mpMRI and negative 18F-PSMA PET: The proportion of clinically insignificant PCa
Time point(s)	day 0: 18F-PSMA PET/MRI day 90 (+/- 90): prostate biopsy	
Phase	Phase II	
Trial Design	Monocentric, single-arm, prospective	

Trial Population	Men with clinical suspicion of csPCa.
Inclusion Criteria	1) Men at least 18 years of age referred with clinical suspicion of prostate cancer candidate for prostate biopsy 2) Feasibility to undergo all procedures listed in protocol 3) Ability to provide written informed consent
Exclusion Criteria	1) Prior diagnosis of prostate cancer 2) Contraindication to MRI (e.g. claustrophobia, pacemaker, estimated GFR lower or equal to 50mls/min) 3) Contraindication to prostate biopsy
Intervention(s)	
IMP(s)	18F-PSMA, 4 MBq/Kg, intravenous administration
NIMP(s)	Not applicable.

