6. OBJECTIVES AND ENDPOINTS

Objectives	Endpoints	Time point(s)
Primary Objective To assess the accuracy and the predictive value of fully hybrid ^{18}F -PSMA PET/MRI for the diagnosis of csPCa	Primary Endpoint Diagnostic accuracies of ^{18}F -PSMA PET and mpMRI will be calculated by means of sensitivity: true positive/(true positive + false negative) and specificity: true negative/(false positive + true negative) using the prostate biopsy result as reference standard.	PET/MRI examination at day 0, and biopsy at day 1-30 (within a month from imaging study)
Secondary Objectives To compare the proportion of csPCa missed by ^{18}F -PSMA PET scan or mpMRI alone	Secondary Endpoints The proportion of csPCa (defined by analysis of prostate biopsy cores, ISUP grade equal or higher than 2) missed by PSMA PET scan or mpMRI alone will be calculated.	PET/MRI examination at day 0, and biopsy at day 1-30 (within a month from imaging study)
Exploratory Objectives To assess the proportion of unnecessary biopsies potentially spared	Other Number of clinically insignificant PCa (ISUP grade 1) identified combining mpMRI and ^{18}F -PSMA PET.	PET/MRI examination at day 0, and biopsy at day 90 (+/-90)

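### The planned figure for biopsies spared is the ISUP 1 share of mpMRI-positive, PET-negative men: it leaves out benign biopsies and is not tied to the significant cancers missed in the same men

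*Combined protocol and SAP*

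**What the plan says.** Section 8 (Trial Design) sets the analysis population and the numerator: "only patients with positive mpMRI and negative 18F-PSMA PET scan will be considered for the analysis and the proportion of clinically insignificant PCa detected". The next sentence gives the interpretation: "In this way we will identify proportion of unnecessary prostate biopsies that could have been spared, thus reducing overdiagnosis".

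The synopsis carries the same quantity as secondary endpoint 2: "Only in patients with positive mpMRI and negative 18F-PSMA PET: The proportion of clinically insignificant PCa". The objective behind it has two parts. The first is "To report the reduction in the detection of clinically insignificant PCa when combining mpMRI and 18F-PSMA PET", and the second is presented as following from it: "and consequently the proportion of unnecessary biopsies potentially spared".

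Section 6 treats the matter differently. The objective "To assess the proportion of unnecessary biopsies potentially spared" is listed as exploratory, and its endpoint is a count: "Number of clinically insignificant PCa (ISUP grade 1) identified combining mpMRI and" PET. This entry is also where clinically insignificant is defined as ISUP grade 1.

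Missed csPCa is planned separately, for each modality over the whole cohort. Synopsis secondary endpoint 1 is "The number of csPCa missed by PET and MR imaging when read independently", and section 16.1 compares the two modalities with a McNemar test. Section 16.1 gives no analysis for the spared-biopsy endpoint.

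**The concern.** When a triage test is used to omit biopsies, two quantities matter in the men it would leave out: how many biopsies would have found no csPCa, and how many would have found it. The planned proportion gives neither. A man with a benign biopsy is as much a potential saving as a man with ISUP 1, but he is not in the numerator. A man with csPCa is the cost of the rule, but among the men who are not ISUP 1 the figure cannot tell him from a benign man.

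This matters because section 8 speaks of reducing the overall number of biopsies and makes avoiding one depend on csPCa being very unlikely. The csPCa count in the mpMRI-positive, PET-negative men is the direct test of that condition. If only the ISUP 1 share is reported under the label of biopsies spared, the reader cannot judge the size of the saving or whether the condition is met.

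**Working it through.** **Inputs from the documents.** N = 167 and csPCa prevalence 56% (section 16.2); csPCa is ISUP 2 or higher and clinically insignificant is ISUP 1 (section 6).

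**The plan's own figure.** The documents give no figure for biopsies spared. The sample size does reproduce: 1.96² × 0.96 × 0.04 / 0.04² = 92.2, rounded up to 93 csPCa cases; 93 / 0.56 = 166.07, rounded up to 167. Expected csPCa is 0.56 × 167 = 93.52.

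**Algebra.** Let the subset hold S men, made up of B benign, I with ISUP 1 and C with csPCa, so S = B + I + C.
- Planned figure, with all subset men as denominator: I/S.
- Biopsies avoided without missing csPCa: (B + I)/S = 1 − C/S.
- Understatement: (B + I)/S − I/S = B/S, the benign share.
- Sensitivity lost against mpMRI alone, with mpMRI-negative men handled alike under both rules: C/93.52.

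For a given I/S, the split of the remaining men between B and C is free. The planned figure therefore fixes neither the saving nor the cost.

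**Illustration.** The documents give neither the size of the subset nor its histology. Assume S = 30 and I = 9. Intervals are exact (Clopper-Pearson) 95%.

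| | C = 0 (B = 21) | C = 6 (B = 15) |
|---|---|---|
| Planned figure, 9/30 | 30% (14.7–49.4) | 30% (14.7–49.4) |
| Non-csPCa, (B + I)/30 | 30/30 = 100% (88.4–100) | 24/30 = 80% (61.4–92.3) |
| csPCa forgone, C/30 | 0% (0–11.6) | 20% (7.7–38.6) |
| Sensitivity lost, C/93.52 | 0 points | 6.4 points |

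**Range.** With ISUP 1 held at 30%, the csPCa share can lie anywhere from 0 to 70%. The understatement B/S then runs from 70 points (no csPCa) down to 0 (no benign men). At that last extreme C = 21, and the sensitivity lost is 21/93.52 = 22.5 points.

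**One common denominator.** Take C = 6 and assume 100 to 140 mpMRI-positive men. ISUP 1 is 9/100 to 9/140, or 9.0% to 6.4%. All non-csPCa biopsies avoided are 24/100 to 24/140, or 24.0% to 17.1%. csPCa forgone is 6/100 to 6/140, or 6.0% to 4.3%.

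**Does secondary endpoint 1 supply the cost?** Not by itself. The csPCa missed by PET is C plus the csPCa in men negative on both tests. A total of 10 missed by PET is compatible with C = 0, 6 or 10, that is, a loss of 0, 6.4 or 10.7 points. C itself is one discordant cell of the McNemar table, so it can be obtained.

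**Denominator.** All men in the subset is the natural reading, but it is not spelled out. If only cancers counted, the example would give 9/9 = 100% with C = 0 and 9/15 = 60% with C = 6.

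**The case against.** The best defence is that the ISUP 1 numerator is deliberate. The main hypothesis in the synopsis confines the biopsies to be reduced to those in men with indolent, low-risk cancer, and the interpretive sentence in section 8 ends on overdiagnosis. A reader might infer that the endpoint contradicts the trial's hypothesis. It does not, because on that wording an ISUP 1 share is a fair measure. The mismatch is with the wider aim in section 8 (fewer biopsies overall, in men very unlikely to have csPCa) and with the label of biopsies spared.

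A reader might also infer that the plan hides the cost of the rule. That is too strong. Missed csPCa is a named secondary endpoint, and the McNemar test cannot be run without counting csPCa in mpMRI-positive, PET-negative men. What is missing is a commitment to show that count beside the saving.

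A third tempting reading is that the sparing analysis breaks the trial's only definition of a positive test. Sections 8 and 10.6 do have an and/or wording for the combined test, under which these men are positive. But they also define positivity for PET and for mpMRI separately, and section 8 sets out each patient group. It says openly that this analysis looks at adding PET to mpMRI for triage, and studying a second rule is legitimate. No section pairs the saving with accuracy computed on the and/or wording; the point is only that nobody should.

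Finally, the endpoint is secondary or exploratory, has no decision rule and did not drive the sample size. That limits the weight of the point but does not remove it.

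**Conclusion.** The point holds, as a gap in analysis and reporting that should be fixed. The planned proportion answers the overdiagnosis question. It does not measure biopsies spared in the wider sense of section 8, and it cannot show whether these men are at very low risk of csPCa. It understates the saving by exactly the benign share of the subset, so only if at least one of these men is benign.

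That the figure determines neither saving nor cost is algebra and needs no assumption beyond taking all subset men as denominator. The sizes do need assumptions: 30 men, 9 with ISUP 1, and 0 or 6 with csPCa are chosen for illustration, and only the 93.5 expected csPCa comes from the plan's own inputs. With ISUP 1 at 30%, the understatement may be anything from 0 to 70 points; the documents support no narrower range.

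The different status and form of the endpoint in the synopsis (secondary, a subset proportion) and in section 6 (exploratory, a number) is a separate inconsistency that should be settled at the same time.

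**What to change.** 1. Add to section 16.1 a table for mpMRI-positive, PET-negative men with biopsy results: counts of benign, ISUP 1 and ISUP 2 or higher, as proportions of the subset and of all mpMRI-positive men. Two-sided 95% intervals are already planned; exact ones suit a subset of this size but are a preference. State how many men in the subset lack histology, since under section 12.2 men who withdraw after the scan are not replaced.
2. Report biopsies avoided as benign plus ISUP 1, always beside the csPCa missed in the same men and the resulting change in sensitivity against mpMRI alone. Do not set this saving beside accuracy computed on the and/or wording, which classes these men as positive.
3. Keep the ISUP 1 share, but label it as insignificant-cancer diagnoses avoided.
4. Reconcile the synopsis, section 6 and section 8 on quantity (proportion or number), denominator, and secondary or exploratory status.

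The cost is some wording and one extra table. The design biopsies every man, so no new data and no change in sample size are needed. The downside for the sponsor is that missed csPCa becomes visible beside the saving. On a fixed denominator, adding benign biopsies can only raise the saving or leave it unchanged. This changes analysis and reporting only and does not say who should be biopsied.

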16. STATISTICS

16.1. Description of Statistical Methods

Diagnostic accuracies of 18F-PSMA PET and mpMRI will be calculated by means of sensitivity: true positive/(true positive + false negative); specificity: true negative/(false positive + true negative); PPV: true positive/(true positive + false positive); and NPV: true negative/(true negative + false negative) using the prostate biopsy result as reference standard.

- The assessment of quantitative imaging parameters, including radiomic features and conventional parameters, characterizing regions of csPCa will be performed by generalized Linear Mixed Models for binary responses. Logistic regression will be used for evaluating PET and MRI parameters and texture features in predicting the presence of csPCa, as defined by biopsy results. To assess the diagnostic performance of PET and MRI parameters, ROC curve analysis will be performed to select optimal cut-offs in predicting the presence of csPCa, as defined by cytological examination, and the corresponding diagnostic accuracy values will be computed.
- McNemar test will be used to compare the proportion of csPCa missed by 18F-PSMA PET or mpMRI alone (12).
- All statistical analyses and data processing will be performed using the R statistical package or the SPSS software. All p-value will be rounded to three decimal places. Statistical significance will be declared if the rounded p-value will be less than 0.050. Two-sided 95% confidence intervals will be calculated.

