16.2. Sample Size Determination

The sample size was computed based on sensitivity analysis for the detection of clinically significant PCa. Assuming an average prevalence of clinically significant PCa of 56%, a total sample size of 167 patients is sufficient for evaluating a sensitivity of 96% with an absolute precision of 4% (at 95% confident level).

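### The 'biopsies spared' analysis uses mpMRI-positive/PET-negative men alone, so it cannot show that adding PET helps, and it does not set the csPCa forgone beside the biopsies spared

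*Combined protocol and SAP*

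**What the plan says.** Section 8 restricts the spared-biopsy analysis: "only patients with positive mpMRI and negative 18F-PSMA PET scan will be considered for the analysis". The proportion of clinically insignificant cancer in that subset is assessed, and the text concludes: "In this way we will identify proportion of unnecessary prostate biopsies that could have been spared, thus reducing overdiagnosis".

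In the synopsis, secondary objective 2 is "To report the reduction in the detection of clinically insignificant PCa when combining mpMRI and 18F-PSMA PET", and its endpoint is "Only in patients with positive mpMRI and negative 18F-PSMA PET: The proportion of clinically insignificant PCa".

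The section 6 table differs. It lists the spared-biopsy question as exploratory and measures it by the number of ISUP 1 cancers identified with the two modalities combined.

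None of these places gives a threshold, a comparator or a decision rule. Section 16.1 plans sensitivity, specificity, PPV and NPV for PET and mpMRI, a McNemar test on csPCa missed by either modality alone, and a general rule: "Statistical significance will be declared if the rounded p-value will be less than 0.050. Two-sided 95% confidence intervals will be calculated". It has no analysis specific to the spared-biopsy endpoint. Section 8 also says that every man is biopsied whatever his imaging shows.

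**The concern.** The conclusion is about what PET adds to mpMRI, but it rests on one cell of the mpMRI-by-PET table. If PET carries no information on histology beyond mpMRI, PET-negative men are a random draw from the mpMRI-positive men. Their ISUP 1 proportion then estimates the rate in all mpMRI-positive men. Nothing in the cell separates that case from a useful PET, and the count of spared ISUP 1 cancers cannot fall below zero.

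The same men may also have csPCa. A triage rule that spares their biopsies forgoes those diagnoses, yet the endpoint reports only the ISUP 1 share.

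Reducing unnecessary biopsies is half of the main hypothesis in the synopsis, so a published spared-biopsy proportion could be read as evidence for PET when it is not.

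**Working it through.** **Inputs from the documents.** N = 167, csPCa prevalence 56%, sensitivity 96% "with an absolute precision of 4% (at 95% confident level") (section 16.2); two-sided 5% level (section 16.1).

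**Plan's own figure.** 1.96² × 0.96 × 0.04 / 0.04² = 92.2, rounded up to 93 men with csPCa. 93 / 0.56 = 166.07, rounded up to 167. The sample size reproduces. It concerns sensitivity only and does not size the spared-biopsy analysis.

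**Inputs assumed, because the documents give none.** m = mpMRI-positive rate, 50–80%; q = PET-negative rate among mpMRI-positive men, 10–50%; r = ISUP 1 rate among mpMRI-positive men, 5–30%.

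**Step 1: uninformative PET.** With PET independent of histology, the expected subset size is 167mq, the expected ISUP 1 count is 167mqr, and the expected proportion is r, whatever q is. If 'favourable' means at least one ISUP 1 man (an assumption), its probability is 1 − (1 − mqr)^167.

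| m / q / r | Subset | Expected ISUP 1 | P(at least one) |
|---|---|---|---|
| 50 / 10 / 5% | 8.4 | 0.4 | 34% |
| 60 / 15 / 10% | 15.0 | 1.5 | 78% |
| 70 / 30 / 15% | 35.1 | 5.3 | 99.5% |
| 80 / 50 / 30% | 66.8 | 20.0 | about 100% |

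The answer depends on the assumed rule. Over the same ranges, requiring an observed proportion of at least 10% gives about 5–100%. Requiring an exact 95% lower limit above 5% gives about 1–100%.

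**Step 2: csPCa in the subset.** If the 56% prevalence also held among mpMRI-positive men (an assumption), an uninformative PET would leave 167 × 0.6 × 0.2 × 0.56 = 11 csPCa in a subset of 20 men, and 167 × 0.8 × 0.4 × 0.56 = 30 in a subset of 53.

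**Step 3: what section 16.1 would show.** Assume 75% mpMRI-positive (125.25 men), 70% of them with csPCa (87.7). With 56% prevalence overall (93.5), about 5.8 csPCa are in mpMRI-negative men.
- PET negative in 30% regardless of histology: 0.30 × 87.7 = 26 csPCa missed by PET alone, against at most about 6 by mpMRI alone. PET sensitivity is at most (93.5 − 26.3)/93.5 = 72%, against 87.7/93.5 = 94% for mpMRI. Exact McNemar p at 26 v 6 is about 0.0005.
- PET negative in 40% of csPCa and 20% of the rest: 35 against at most 6. PET sensitivity is at most 63%, and p is about 0.000005.

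A poor PET would therefore be visible, though in a different table.

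**Step 4: is a contrast enough?** Same setting, with PET negative in 15% of csPCa and 50% of the 37.6 men without csPCa. PET-negative men: 0.15 × 87.7 = 13.2 with csPCa and 0.50 × 37.6 = 18.8 without, so 13.2/31.9 = 41% csPCa. PET-positive men: 80% csPCa. A two-sided Fisher test detects this in about 97% of simulated trials, yet about 13 csPCa are forgone for about 19 biopsies avoided. The contrast shows discrimination but does not show that sparing is acceptable.

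**Step 5: behaviour of the contrast.** Simulated with 4,000 trials per scenario, mpMRI-positive 60–80%, PET-negative 20–40% of these. With an uninformative PET, Fisher rejects in about 2–5% of trials. Power for non-csPCa 70% v 30% (PET-negative v PET-positive) is 89–99%; for 60% v 35% it is 49–79%.

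**The case against.** The strongest reply is that this is the right cell. Among mpMRI-positive men, only the PET-negative would have their biopsy spared; PET-positive men would be biopsied either way. A count of avoided procedures cannot be negative, and the endpoint is descriptive: the synopsis says it is to be reported. This stands for the size of the spared set, and the fix keeps that set. It does not cover the further step to reduced overdiagnosis by adding PET, which section 8 takes without a comparator.

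Two stronger readings are tempting, and the documents support neither.

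A reader might infer that a useless PET would be declared a success in some fixed, high share of trials. The plan has no success rule and gives none of the rates required, so any such share depends on an assumed rule and assumed rates.

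A reader might also infer that a poor PET would pass unnoticed. It would not. The reads are blinded to each other, and csPCa in mpMRI-positive/PET-negative men is one of the two discordant cells of the McNemar test, so those cancers must be counted. Step 3 shows how plainly they would appear. What section 16.1 does not give is PET negativity among mpMRI-positive men without csPCa, or any link from missed csPCa to the spared-biopsy statement.

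**Conclusion.** The concern holds as an interpretive gap in a secondary (or exploratory) endpoint. The ISUP 1 proportion in mpMRI-positive/PET-negative men cannot show that adding PET helps, because its expected value under an uninformative PET is simply the rate in all mpMRI-positive men. That follows from the definition and needs no assumed rate. It also leaves out the csPCa forgone in the same men.

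The size is conditional. Under an assumed rule of at least one ISUP 1 man, an uninformative PET looks favourable in about 34% to 100% of trials over the assumed ranges, and in 99.5% at 70/30/15%; stricter rules give much lower minima. The primary accuracy analysis and the McNemar comparison are not affected.

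**What to change.** In section 8, synopsis secondary endpoint 2 and section 16.1:

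1. Keep mpMRI-positive/PET-negative men as the set whose biopsies would be spared, but tabulate csPCa, ISUP 1 and benign histology by PET result in all mpMRI-positive men.
2. Report (a) within mpMRI-positive/PET-negative men, the non-csPCa biopsies avoided beside the csPCa forgone, each with a two-sided 95% CI; and (b) the PET-negative minus PET-positive difference in csPCa proportion with its two-sided 95% CI.
3. Attribute a spared-biopsy or reduced-overdiagnosis statement to PET only when (b) supports discrimination. Always give it together with the csPCa forgone from (a), never from the ISUP 1 proportion alone.
4. Reconcile the endpoint's status and measure: secondary, with a subset proportion, in the synopsis; exploratory, with a different count, in section 6.

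The cost is wording and one extra table. All men are imaged and biopsied, so no further patients, readers or procedures are needed. The downsides are a less automatic favourable statement and modest power for smaller differences (49–79% for 60% v 35%), so (b) may be inconclusive in a trial sized for the precision of sensitivity.
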